5. Intervention feasibility: measured with the Feasibility of Intervention Measure, in which participants respond to 4 questions on a 5-point Likert scale from 1=completely disagree to 5=completely agree at the end of the intervention [37].

Acceptability Outcomes

A semistructured interview guide will be used to assess the acceptability of study procedures as well as the acceptability and satisfaction with the CSM-IBD. For instance, questions will probe for clarity of instructions, the burden of study procedures, and satisfaction with intervention content and delivery. Transcripts from participant interviews will be coded by 2 individuals using open coding methods to evaluate intervention acceptability. The use of CSM-IBD strategies will be assessed at 3 months post intervention by asking participants how often they use each strategy, with response options as: not at all or rarely, occasionally (at least 1 day a week), often (at least 2 days a week), very often (at least 4 days a week), or almost always [38]. Participants will complete the Acceptability of Intervention Measure, which includes 4 questions rated on a 5-point Likert scale from 1=completely disagree to 5=completely agree [37]. Satisfaction will also be measured with the 8-item Client Satisfaction Questionnaire [39].

Primary Outcomes

Quality of Life

The SIBDQ is a 10-item questionnaire that evaluates the quality of life. Participants respond on a 7-item Likert scale from all the time to none of the time. Total score range: 10 to 70 [40].

Symptoms

Symptoms are measured using a numeric rating scale where participants report the severity of the symptom from 0=not present to 10=worst possible. Symptoms include abdominal pain, anxiety, bloating, constipation, depression, diarrhea, fatigue or tiredness, passing gas, sleepiness during the day, stress, and urgency.

Secondary Outcomes

1. Process variables [41,42]
 - Self-Efficacy for Managing Chronic Disease: a 6-item self-report scale. Participants report ranging from not at all confident to totally confident [21].
 - Index of Self-Regulation: a 9-item scale to measure an individual's level of self-regulation [43].
 - Patient Activation Measure: a 13-item scale that assesses patients' beliefs, knowledge, and confidence in managing their health [44,45].

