2. Biological signatures: stool samples will be collected by participants and stored immediately in home freezers (-20°C) before transport to the UW School of Nursing Biobehavioral Laboratory. Samples will be stored at -80°C until batch processing.
 - Gut microbiome: fecal microbial communities will be characterized using metagenomic shotgun sequencing on the Illumina MiniSeq or NextSeq platforms (Illumina, Inc) [46,47].
 - Fecal calprotectin: fecal calprotectin is a biomarker used to measure inflammation in the gut and will be assessed using an enzyme-linked immunosorbent assay [48].
3. Socioecological factors were selected based on the National Institute for Nursing Research's common data elements and include sex, gender, age, race or ethnicity, education level, employment, marital or partner status, household size, and neighborhood (urban or rural, zip code). Dietary intake can influence the composition of the gut microbiome and symptoms [49]. At the time of the stool collection, subjects will complete a detailed 3-day food record (Fred Hutchinson Cancer Research Center Nutrition Assessment).
4. The clinical phenotype will be obtained from the electronic medical record: type of disease, time since diagnosis, history of bowel surgery, disease distribution (measured by

the Montreal Classification), medications, and disease activity (Harvey Bradshaw Index for Crohn Disease [50] and Simple Colitis Activity Index for Ulcerative Colitis [51]; <5 indicates remission).

5. Health care use will be evaluated from the electronic medical record and patient self-report, including emergency department use, hospitalizations, outpatient visits, laboratory tests, imaging, and procedures, as well as providers' nonclinical time spent managing patients.

Participant Timeline

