80% power. For aim 3, there will be 80% power to detect a correlation of 0.45. As a pilot study, the project is not powered to detect differences or correlations unless they are large.

Recruitment

Overview

Participant recruitment will take place at the UW Inflammatory Bowel Disease Clinics. The UW sees a large number of patients with IBD and serves as a tertiary care clinic for patients with IBD in the Washington, Oregon, Alaska, Montana, and Idaho regions. Recruitment may occur in three different settings: (1) in a clinic, (2) virtually (via telephone, email, or mail), and (3) by posting on the Institute of Translational Health Sciences website. All individuals will be informed that participating or not participating will not influence the care that they receive.

In a Clinic

Weekly prescreening will occur to determine if participants with scheduled IBD clinic appointments may be eligible for the study. The goal of prescreening is to enable purposeful sampling of patients based on demographic (eg, age and race) and disease characteristics (eg, disease activity). Individuals who are eligible will receive a flyer containing the study purpose and contact information from either their health care provider or study staff (depending on feasibility and current COVID-19 restrictions). Individuals will have time to review the study information. Participants can call study staff or complete a REDCap survey to express their interest and complete screening questions.

Virtually

The team may contact potential participants via phone, email, or mail if in-person recruitment becomes difficult or not feasible. All contact will follow the UW's institutional review board guidelines for cold contact recruitment. Those expressing interest in the study will call study staff for more information and then complete additional screening questions.

Institute of Translational Health Sciences Website

Information regarding the study will be posted on the UW Institute of Translational Health Sciences website. Interested individuals can complete the contact form to be contacted by study staff and can complete screening questions digitally.

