In all instances, the purpose of the study, study design, and length of time to complete the study will be discussed. To assess participants' understanding of study procedures, individuals will be asked to briefly describe the study. Interested individuals will complete additional screening questions to confirm whether patients meet the specified inclusion and exclusion criteria.

Screening questionnaires may be completed over the phone or electronically via REDCap, based on patient preference. Those meeting inclusion or exclusion criteria will be invited to participate in the study, sign a consent form, and begin data collection. Throughout the entire process of

informed consent, from the first contact with the patient, the potential participants are able to ask any questions or delay making a decision. This screening and recruitment process will continue until the target sample size has been reached.

Intervention Allocation

A computer adaptive randomization procedure using a modification of the minimization method proposed by Pocock and Simon [55] will be used to balance groups based on SIBDQ at baseline. Once the data are entered into the computer, the computer program will return the participants' group assignment.

Statistical Analysis

Feasibility

The number and percentage will be calculated for participants who were prescreened, approached, screened, and enrolled (recruitment). We will assess dropout rates between the CSM-IBD and usual care (randomization). Quality of data will focus on the data completeness of questionnaires; missing data will be reported, and bivariate comparisons will be made between individuals with and those without missing data (data collection). We will report how many participants collected biological samples within the desired timeframe (sample collection). The mean and SD will be reported for the Feasibility of Intervention Measure (intervention feasibility).

Acceptability

Transcripts from participant interviews will be coded by 2 individuals using open coding methods (acceptability and satisfaction). In addition, numbers and percentages will be reported for participants who continue to use self-management strategies 3 months post intervention.

Primary Outcomes

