Data from the 2 follow-up time points (immediate and 3 months post intervention) will be analyzed together using linear mixed models for each of the outcomes. For example, one model will have a change in the quality of life from baseline to immediate and 3 months post intervention as the outcomes, subject as a random effect, time (immediate or 3 months) as a within-subject fixed factor, and treatment group as an across-subject fixed factor. Baseline quality of life will be included as a covariate in the model, as will any baseline variables that differ between the 2 treatment groups. The parameter for the treatment group factor will provide an estimate of the treatment effect, that is, the difference between the treatment groups in mean change in the quality of life, and a 95% CI on the estimated difference will be computed. We hypothesize participants in the CSM-IBD will report a greater reduction in symptoms compared to those in usual care. A second model will also include an interaction between group and time to test whether the treatment effect is different at the 2 post intervention times. Additional analyses will estimate treatment effects separately for men and women.

Secondary Outcomes

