Study data will be collected and stored on REDCap. Participants will be assigned a unique study identification number. Only study members will have access to the data through a password-protected system and will have access to the least amount of data required for their position using limitations in REDCap user rights. The study will use ongoing quality control procedures during data collection, storage, and processing, including the use of the REDCap data quality module.

Ethics Approval

The institutional review board at the UW approved this protocol (STUDY 00015210) and determined the study to be minimal risk. This study is registered in ClinicalTrials.gov

(NCT05651542). Any amendments to the study will be reviewed by the institutional review board and subsequently updated in the ClinicalTrials.gov registry. Participants in the usual care group will be offered access to the CSM-IBD intervention after they complete the 6-month data collection.

Dissemination

Study findings will be disseminated through presentations and publications to clinicians and researchers. Findings will be reported to the community through lay presentations and social media. Individuals will be eligible for authorship based on the International Committee of Medical Journal Editors' recommendations. The study will provide the basis for future research on self-management interventions. The findings of the study will be used to refine the intervention and develop a full-scale trial with additional recruitment sites throughout diverse geographical regions.

Patient Involvement

This study is informed by a patient advisory group that was convened for the purpose of providing advice and oversight for the study.

Results

This pilot randomized controlled trial was funded by the National Institute of Nursing Research (K23NR020044) in April 2022. Recruitment began on February 20, 2023. As of April 2023, we have enrolled 4 participants. We expect the study to be completed by March 2025.

Discussion

Expected Findings

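### Mixed-model covariates are chosen by observed baseline imbalance, and the minimisation factor (SIBDQ) is fixed only in the quality-of-life model

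*Combined protocol and SAP*

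**What the plan says.** Statistical Analysis, Primary Outcomes, analyses both follow-up times together "using linear mixed models for each of the outcomes". It writes out the quality-of-life model as the example: change from baseline as outcome, a random subject effect, and time and group as fixed factors. Baseline quality of life is a covariate, "as will any baseline variables that differ between the 2 treatment groups". The document does not say how a difference is judged, which variables are screened, or how many may enter.

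Intervention Allocation names one balancing factor: the minimisation procedure "will be used to balance groups based on SIBDQ at baseline". SIBDQ is also the quality-of-life outcome, so in that model it enters as the outcome's own baseline. No section lists covariates for the 11 symptom ratings ("Symptoms include abdominal pain, anxiety, bloating, constipation, depression, diarrhea, fatigue or tiredness", and four more).

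**The concern.** Under random allocation an arm difference at baseline is a chance event and says nothing about whether the variable predicts the outcome. Selecting on it lets in variables that only use up degrees of freedom and share information with the group term, and it passes over prognostic variables that happen to be balanced. The model is unknown until baseline data are compared by arm. With 'differ' undefined, two analysts could both follow the text and report different treatment effects.

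The rule also works against the allocation scheme. Minimisation makes SIBDQ the variable least likely to differ, so the rule screens out the one variable the design chose to balance. If SIBDQ predicts symptom change beyond the symptom's own baseline, a model without it overstates the standard error of the group difference.

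The estimate and its 95% interval are the aim 2 result, and "The findings of the study will be used to refine the intervention and develop a full-scale trial". Sample Size concedes that "the project is not powered to detect differences or correlations unless they are large", so there is little precision to spare.

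**Working it through.** **The plan's own figure.** Sample Size gives a detectable effect of 0.81 at 80% power with 36 and 18 participants. Two-sided 5%, normal approximation: (1.960 + 0.842) × √(1/36 + 1/18) = 2.802 × 0.2887 = 0.809. It reproduces (power at 0.81 is 80.1%, or 78.6% by noncentral t) and uses no covariates.

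**Candidate pool, counted from Study Outcomes and the analysis section.** Socioecological: "sex, gender, age, race or ethnicity, education level, employment, marital or partner status, household size, and neighborhood", 9 variables. Clinical: "type of disease, time since diagnosis, history of bowel surgery, disease distribution", plus medications and disease activity, 6 variables. Total 15. Adding 3 process scales, calprotectin, 3 microbiome summaries, protein and fibre gives 24. For a symptom model, the other 10 symptoms give 34.

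**Chance that at least one enters.** If 'differ' means p < 0.05 and candidates are independent, this is 1 − 0.95^k: 53.7% for k = 15, 70.8% for 24, 82.5% for 34. With pairwise correlation 0.3, simulation gives 46%, 60% and 69%.

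**Effect on power and interval width.** Assumptions: baseline-outcome correlation 0.6 and effect 0.65 SD. The residual SD is √(1 − 0.36) = 0.8, so the effect is 0.65/0.8 = 0.81 residual SDs, in line with the plan. Simulation: 54 participants, 2:1, minimised on SIBDQ in 4 categories with a 0.9 biased coin, SIBDQ correlated 0.5 with the symptom baseline, 5,000 runs. The analysis is ANCOVA on the mean of the two follow-ups, which with complete data equals the group term of the random-intercept model. With non-prognostic candidates:

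| Pool | Own baseline only | Plan's rule | Loss (points) |
|---|---|---|---|
| 15, independent | 79.2% | 75.9% | 3.3 |
| 24, independent | 78.7% | 73.5% | 5.2 |
| 34, independent | 78.1% | 71.0% | 7.1 |
| 15, correlated 0.3 | 78.2% | 76.0% | 2.2 |
| 24, correlated 0.3 | 78.2% | 74.3% | 3.9 |
| 34, correlated 0.3 | 78.4% | 73.5% | 4.9 |

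Mean interval width with own baseline only is 0.93 SD (check: 2 × 2.008 × 0.8 × 0.2887 = 0.927). Under the rule with independent pools it is 0.97, 0.99 and 1.01 SD, that is 4%, 6% and 9% wider; with correlated pools it is 3 to 7% wider. Type I error under the rule is 4.7 to 5.3%.

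**If some candidates are prognostic** (3 with coefficient 0.35): pool of 10, 78.2% to 78.7% (fixed 36:18 arms, no minimisation); pool of 15, 78.4% to 78.3%; pool of 24, 79.1% to 75.5%.

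**Movement of the estimate.** When any variable enters, the treatment estimate shifts by a median 0.06 to 0.08 SD.

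**SIBDQ in a symptom model.** Pool of 15, correlated 0.3, non-prognostic. The fix is the symptom's own baseline plus SIBDQ, with no selection:

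| Partial correlation of SIBDQ | Plan | Fix | Part due to SIBDQ alone (points) |
|---|---|---|---|
| 0 | 76.0% | 77.9% | −0.3 |
| 0.3 | 77.0% | 82.3% | +2.4 |
| 0.5 | 76.4% | 88.4% | +8.7 |

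Omitting a balanced covariate with partial correlation r widens the interval by about 1/√(1 − r²): 1.00, 1.05 and 1.15. Type I error without SIBDQ is 4.8%, 4.7% and 3.8%. SIBDQ met p < 0.05 in fewer than 0.1% of trials. With 2 SIBDQ categories and a 0.8 coin, SIBDQ alone contributes −0.7, +3.1 and +8.2 points and differs in 0.2 to 0.4% of trials.

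**The case against.** - **Most of the model is fixed, and the rule uses baseline data only.** It could be applied before any outcome is seen, and mechanical use does not inflate type I error. This stands. It does not cover an undefined threshold: in a separate simulation (15 candidates, 3 prognostic at 0.4), taking the most favourable of no adjustment or thresholds of 0.05, 0.10 and 0.20 raised type I error to about 7%.
- **The symptom models are unspecified, not expressly without SIBDQ.** True: the quality-of-life model is introduced as an example. By its pattern a symptom model would carry the symptom's own baseline, and nothing adds SIBDQ. Either reading calls for the same clarifying sentence.
- **The larger figures rest on inputs the document does not give.** This stands. The gain of 8.7 points needs a partial correlation of 0.5, and at 0 there is none. The plan-against-fix contrast also combines two changes and uses non-prognostic candidates, the case least favourable to the plan. With only 5 to 8 candidates screened, the loss is 1.0 to 1.7 points. Disease activity and medications could be prognostic, which would shrink or remove the loss.
- **Movement of the estimate is not all harm.** Correct: the largest shifts (90th percentile near 0.26 SD) arise with prognostic candidates, where adjustment removes real chance imbalance. With non-prognostic candidates in pools up to 24, the 90th percentile is 0.13 to 0.17 SD.
- **It is a pilot.** Feasibility comes ahead of efficacy and no sample size changes. That limits the weight of the point but does not justify the rule.

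**Conclusion.** The concern holds, as a change that should be made rather than one on which the trial depends. The plan states a covariate rule driven by chance imbalance, without a threshold or candidate list, and does not carry its only minimisation factor into the symptom models. Neither feature inflates type I error when applied mechanically. The harm is a model open until arms are compared, plus lost precision: 2 to 7 power points with 15 to 34 non-prognostic candidates, nothing or a 0.5-point gain with 3 prognostic candidates in a pool of 10 to 15. For SIBDQ in the symptom models the effect runs from nil to about 9 points, according to a partial correlation that the document does not give. Confidence is high on the rule and on the gap, and conditional on these assumptions for the sizes.

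**What to change.** Replace the clause on differing baseline variables with:

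> Each aim 2 model will include the baseline value of its outcome and baseline SIBDQ, the minimization factor (one and the same variable in the quality-of-life model). No covariate will be added because of an observed baseline difference. Such differences will be described, and any further adjustment will be reported as a labelled sensitivity analysis.

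SIBDQ is already collected at baseline, so no data or sample size changes. Results reports 4 participants enrolled as of April 2023; some may already have been allocated, but at that stage the model can be fixed before any meaningful comparison of the arms is possible.

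The price is one degree of freedom per symptom model, 0.2 to 0.5 power points if SIBDQ adds nothing. In that case, with 3 of 15 candidates prognostic at 0.35, the fix gives 77.8% against 78.3% under the plan, about 0.5 point lower. The fix does not capture prognostic variables other than the two it names. If the team believes in others, naming them now would be sound; adding them because they differ would not.

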The objectives of this pilot randomized controlled trial are to (1) determine the feasibility and acceptability of study procedures (recruitment, randomization, and data and sample collection) and CSM-IBD; (2) compare CSM-IBD to usual care on changes from baseline to 3 months post intervention in quality of life and daily symptoms (fatigue, sleep disturbance, psychological distress, gastrointestinal symptoms) among IBD patients and (3) explore the association of socioecological factors (age, sex, race, ethnicity, or diet), clinical phenotype (medications, disease distribution, and disease activity), and biological signatures (microbiome and calprotectin) with symptoms at baseline and response to intervention (post intervention).

Methods

Study Design

The proposed study is a 2-arm pilot randomized controlled trial that follows the Consolidated Standards of Reporting Trials and Standard Protocol Items: Recommendations for Interventional Trials guidelines [30,31]. In a 2:1 ratio, 54 participants will be randomized (intervention=36 participants; usual care=18 participants). This randomization scheme was selected to maximize data collection and information regarding the intervention group. The intervention will take place over 8 sessions. The participants will be blinded to the study hypotheses. Web-based self-reported questionnaires will be used to reduce detection bias.

Theoretical Framework

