All procedures will occur remotely; data collection will occur digitally through REDCap (Research Electronic Data Capture; Vanderbilt University), a secure Health Insurance Portability and Accountability Act (HIPAA)-compliant database [52,53]. Individuals meeting eligibility criteria and interested in the study will be asked to sign a consent form and HIPAA form prior to participating in the study. All participants will complete baseline questionnaires (socioecological factors and disease information). Participants will collect a stool sample at home using a stool sample collection kit (instructions and researcher contact information will be provided); a 3-day food record will be collected starting 2 days before the stool sample collection. The stool samples will be placed in home freezers and returned to the School of Nursing Biobehavioral Laboratory. Participants will be provided with ice packs, a Styrofoam mailing box, and return labels. Stool samples will be stored at -80°C until batch processing.

Following baseline data collection, participants will be randomly assigned to the 8-session CSM-IBD or usual care. Immediately post intervention, participants will complete questionnaires, collect a stool sample, and report a 3-day food record. Three months post intervention, participants will complete questionnaires and participate in a qualitative data collection interview. In addition, participants will report whether or not they are continuing the self-management skills learned in the intervention. Semistructured interviews will be conducted to understand the participants' perspective on procedural burden and suggestions to improve the intervention, including satisfaction with the intervention. Interviews will be recorded and transcribed. Participants will be compensated for each assessment completed (baseline, immediately post intervention, and 3 months post intervention). To increase retention, participants in the usual care group will be provided access to the intervention upon study completion. Participants can continue the study despite not completing all data collection assessments and all intervention sessions.

Sample Size

Based on recommendations for preliminary studies [54], we aim for data on 54 participants (36 intervention and 18 usual care). The sample size is appropriate for assessing feasibility and acceptability (aim 1). For aim 2, we will be able to detect fairly large effect sizes of 0.81 with

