Analyses of microbiome data will use 3 summary measures—Shannon diversity, richness, and *Firmicutes/Bacteroidetes* ratio—as well as the relative abundance of bacterial families (eg, family Ruminococcaceae) and genera and will control for the read count. For diet, we will focus on protein and fiber intake, as our previous work has indicated these may be important dietary intake components related to the gut microbiome. First, we will examine the associations between socioecological, clinical phenotype, and biological signatures with symptoms at baseline in the total sample using Pearson correlation or Spearman rank correlation based on measure distributions. Scatter plots will be used to visually display these associations. Second, we will examine associations between socioecological, clinical phenotypes, and biological signatures at baseline and response to intervention in the intervention group. Response to intervention is conceptualized as an increase of 8 points on the SIBDQ scale (quality of life) [40] or a 50% decrease from baseline in the GI symptom score [27]. Among the intervention group, we will use the *t* test and chi-square test to compare socioecological factors, clinical phenotypes, and biological signatures among patients with and without a response to treatment.

Monitoring

This study has been classified as a minimal-risk study. The principal investigator has the responsibility for study oversight, including patient safety and data quality, as well as submitting reports to the funder and the institutional review board. Due to the low-risk nature of the CSM-IBD, we do not anticipate any adverse events or serious adverse events. The data safety and monitoring team will meet quarterly to review the study. The team will monitor accrual, withdrawals, data quality, timeliness of data submission, protocol compliance, and the types and frequency of adverse events and serious adverse events. No interim analysis or stopping rules are currently planned. However, if any adverse events or serious adverse events are reported, the data safety and monitoring team will meet within a week to discuss the event and any potential changes needed to the study procedures.

Ethics and Dissemination

Data Management

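### The aim 3 microbiome-symptom correlations carry no diet term, and no energy adjustment is stated for protein and fiber, although the plan says diet can influence both microbiome and symptoms

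*Combined protocol and SAP*

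**What the plan says.** All references are to the combined protocol and SAP.

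- **Objectives:** objective 3 is exploratory. It counts diet among the socioecological factors and the microbiome among the biological signatures to be related to baseline symptoms and to response.
- **Study Outcomes, Secondary Outcomes, item 3:** "Dietary intake can influence the composition of the gut microbiome and symptoms". At stool collection, "subjects will complete a detailed 3-day food record".
- **Participant Timeline:** the diet data are matched in time to the stool sample: "a 3-day food record will be collected starting 2 days before the stool sample collection".
- **Statistical Analysis, Secondary Outcomes:** microbiome analyses "will control for the read count". Then: "For diet, we will focus on protein and fiber intake", a choice justified by the team's previous work linking these nutrients to the gut microbiome. Baseline associations with symptoms are examined in the total sample "using Pearson correlation or Spearman rank correlation based on measure distributions". In the intervention arm, responders and non-responders are compared by t and chi-square tests, also without covariates.
- **Statistical Analysis, Primary Outcomes:** the covariate rule (baseline value plus any variables that differ between arms) belongs to the mixed models for aim 2 and does not extend to aim 3.

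**The concern.** There are two linked gaps.

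1. **No diet term.** By the plan's own account, diet may act on both variables that the microbiome-symptom correlation relates. A bivariate correlation cannot separate that shared influence from a direct link. Protein and fiber are chosen because they bear on the microbiome, yet they are left out of the analysis where that matters. This gap needs no assumption about eating behavior.
2. **No energy adjustment.** The scale of protein and fiber intake is not stated. If it is the amount eaten, it will usually rise and fall with total food eaten. If people with worse symptoms also eat less, intake will correlate with symptoms even when no specific nutrient matters.

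At stake is how exploratory associations are read. The Dissemination and Expected Findings sections say the results will be used to refine an intervention that includes diet counseling. Future Directions names the microbiome as a possible predictor of response.

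**Working it through.** **Inputs from the documents:** n = 54 in total, 36 in the intervention arm; 80% power for r = 0.45 (Sample Size). Two-sided alpha of 0.05 is assumed, because none is stated for aim 3. The documents give no diet, energy or microbiome correlations, so every such value below is assumed and shown as a range.

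**1. The plan's own figure.** By Fisher z, power = Φ(atanh(r)·√(n−3) − 1.96), with atanh(0.45) = 0.485.
- n = 36: 0.485 × √33 − 1.96 = 0.82, power 79.5%.
- n = 54: 0.485 × √51 − 1.96 = 1.50, power 93.3%.

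The 0.45 therefore fits the 36 intervention participants. For the total sample, where the baseline correlations are planned, the detectable r is tanh((1.96 + 0.842)/√51) = 0.373.

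**2. Diet as a common cause.** If diet correlates a with a microbiome measure and b with symptoms, and nothing else links the two, the induced correlation is a × b. Rejection counts both tails at n = 54.

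| a | b | induced r | share of studies with p < 0.05 |
|---|---|---|---|
| 0.3 | 0.3 | 0.09 | 10% |
| 0.3 | 0.5 | 0.15 | 19% |
| 0.5 | 0.5 | 0.25 | 45% |

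The partial correlation given diet is (r − ab)/√((1−a²)(1−b²)), which is 0 when r = ab. The same algebra holds if diet is an intermediate step between symptoms and microbiome. Adjustment therefore shows how much of the association diet carries; it does not show which causal account is right.

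**3. Total energy and the intake scale.** Simulation with 400,000 draws; symptoms correlate −0.2 to −0.4 with energy and have no nutrient-specific link. Energy is log-normal with CV 0.25–0.30, and the nutrient component is log-normal with CV 0.15–0.35. The ranges are correlations with symptoms.

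| How nutrient amount depends on energy | amount | per 1000 kcal | amount, adjusted for energy |
|---|---|---|---|
| proportional | −0.11 to −0.34 | 0.00 | about 0 |
| square root | −0.07 to −0.28 | +0.06 to +0.28 | about 0 |
| unrelated | 0.00 | +0.11 to +0.35 | about 0 |

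At n = 54, an induced correlation of size 0.11 is significant in 12% of studies and one of 0.20 in about 30%. Density looks clean only in the first row, where the simulation makes it so by construction. In the other rows it creates an association of opposite sign. Adjusting for total energy gives about 0 in all three.

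**4. Sensitivity to the assumed energy link.** With symptom-energy r of −0.3 to −0.7 and energy-nutrient r of 0.4 to 0.8, the induced r is −0.12 (0.3 × 0.4) to −0.56 (0.7 × 0.8), significant in 14% to over 99% of studies. With no symptom-energy link, rejection stays at 5%. In finite-sample runs at n = 54 (20,000 per scenario), adjusting for energy returned the diet-symptom rejection rate to about 5% in every scenario.

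**5. Cost in precision.** With k covariates, replace n−3 by n−3−k. Detectable r with 80% power:

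| k | n = 54 | n = 36 |
|---|---|---|
| 0 | 0.373 | 0.452 |
| 1 | 0.377 | 0.458 |
| 2 | 0.380 | 0.465 |
| 3 | 0.384 | 0.471 |

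**The case against.** The strongest reply is that this is an exploratory aim in a pilot. The Sample Size section says that only large correlations are within reach and names 0.45. The common-cause values (0.09 to 0.25) lie well below that, and no significance threshold is set for these correlations. This stands as a limit on severity. It does not remove the problem, because smaller correlations will still be estimated and plotted, and some will reach p < 0.05.

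It is also fair to say that diet is singled out: disease activity and medications are aim 3 factors too, and they are equally absent from the correlations. Diet is the one for which the plan itself states an influence on both sides, and the one measured at the stool sample.

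Three stronger readings are tempting, and the documents do not support them.

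- A reader might infer that the plan commits to raw gram amounts. It does not; the scale is left open, so the gap is a missing rule.
- A reader might infer that participants eat less when unwell. The documents do not say so. The mechanism and its size are assumptions, and without it the energy part of the concern disappears while the missing diet term remains.
- A reader might infer that intake per 1000 kcal is the obvious cure. The second table shows that density used alone can reverse the bias.

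Finally, diet may lie on the path between symptoms and microbiome. Adjustment would then remove part of the association being sought. That is a sound reason to show adjusted results beside the unadjusted ones and not in their place.

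**Conclusion.** The point holds as an analysis-plan improvement for aim 3. The plan says diet can influence both microbiome and symptoms, then relates the two by bivariate correlation with read count as the only named control. It states no energy adjustment for protein and fiber.

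Under assumed diet links of 0.3 to 0.5 on each side, diet alone induces r of 0.09 to 0.25, which is significant in roughly one study in ten up to nearly one in two at n = 54. The energy-related bias depends entirely on an assumed link between symptoms and total intake: negligible without it, substantial if it is strong. No figure here is an estimate of what this trial will find.

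A reader might infer that the pilot's efficacy signal is compromised. It is not: the randomized comparison under aim 2 and the feasibility and acceptability outcomes do not use these correlations.

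**What to change.** In Statistical Analysis, Secondary Outcomes, keep the planned unadjusted correlations, state the scale of protein and fiber intake, and add two results beside them:

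1. For diet and symptoms, partial (or partial rank) correlations of protein and fiber with symptoms, adjusted for total energy from the same 3-day food record. Density per 1000 kcal may be shown as well, but not as the only scale.
2. For microbiome and symptoms, partial (or partial rank) correlations or regressions adjusted for protein, fiber and total energy, with read count handled as already planned.

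Label both as exploratory, and note that diet may be a common cause or an intermediate step, so that a change after adjustment is not by itself evidence of confounding. Give the number of participants behind each value.

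The cost is wording and up to three degrees of freedom: detectable r goes from 0.373 to 0.384 at n = 54. Participants without a food record are lost from the adjusted results. The proposal also assumes that total energy can be derived from the food record. That is likely for a detailed record, but the documents do not state it and the study team should confirm it.
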